3 STUDY DESIGN

This is a Phase 3, multi-center, randomized, double-blind, placebo-controlled study in anemic subjects with Stage 3, 4, or 5 CKD who are not on dialysis.

This study will consist of three study periods:

- **Screening Period:** Up to 6 weeks
- **Treatment Period:** Variable for individual subjects. In order to complete the Treatment Period simultaneously for all study subjects, the minimum treatment duration may be less than 52 weeks, with a maximum treatment duration of up to 3 years after the last subject is randomized.
- **Post-Treatment Follow-Up Period:** 4 weeks

3.1 IN ORIGINAL PROTOCOL AND AMENDMENT 1

Following the Screening Period, subjects are randomized to 1 of 6 treatment arms, defined by their dose frequency during maintenance (see Table 1). The randomization will result in a 2:2:2:1:1:1 ratio of subjects receiving roxadustat or placebo, respectively.

Randomization stratification factors include screening Hb values, cardiac/cerebrovascular/thromboembolic medical history, and estimated glomerular filtration rate (eGFR), and geographic region.

The Investigator, study site staff, subject, and the sponsor, are blinded to study drug, but not to dose or dosing frequency. Additionally, all efforts will be made to keep subjects blinded to study Hb values.

Study drug will be dosed TIW for anemia correction until subjects achieve a Hb value of ≥ 11 g/dL and ≥ 1 g/dL increase from baseline at two consecutive visits. Once these criteria are met, a dose frequency conversion to QW or BIW or a continuation of TIW will occur according to the subject's assigned treatment arm at randomization, defining entry into the maintenance phase.

Table 1. Study Drug Dose Frequencies

Treatment Arms	Correction	Maintenance	n (Roxadustat)	n (Placebo)
1A	TIW	QW	100*	0
1P	TIW	QW	0	50*
2A	TIW	BIW	100	0
2P	TIW	BIW	0	50
3A	TIW	TIW	100	0
3P	TIW	TIW	0	50

A=Active, P= Placebo

*These numbers are based on a sample size of 450 and would increase if overall sample size increases.

3.2 UNDER AMENDMENT 2 & 3

Following the Screening Period, subjects will be randomized in a 2:1 ratio to receive roxadustat (approximately 300-800 subjects) or placebo (approximately 150- 400 subjects). Randomization is stratified by the following factors:

- Screening Hb values (≤ 8 g/dL vs > 8 g/dL)
- History of cardiovascular, cerebrovascular or thromboembolic diseases (Yes vs No)
- eGFR (< 30 mL/min/1.73 m² vs ≥ 30 mL/min/1.73 m²)
- Geographic region (US vs Ex-US).

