4.2 SECONDARY ENDPOINTS

The secondary efficacy endpoints in this study are:

- For Ex-US submission only: Hb maintenance: Mean change from baseline (CFB) in Hb averaged over 8 weeks of treatment at Weeks 28 to 36, without rescue therapy within 6 weeks prior to and during this 8-week evaluation period.
- Mean CFB in Hb during the evaluation period (defined as Week 28 until Week 52) in subjects with baseline CRP > ULN
- Proportion (%) of subjects with Hb Level ≥ 10 g/dL between Week 28 to 36, without use of rescue therapy within 6 weeks prior to and during these 8-week evaluation periods.
- Hb maintenance by dose frequency: TIW, BIW, QW
- Mean CFB in LDL cholesterol averaged over Weeks 12 to 28
- Time to (and proportion of subjects who received) rescue therapy (composite of blood/RBC transfusion, ESA use, and IV iron) in the first 52 weeks of treatment
- Mean CFB in SF-36 Vitality subscore averaged over Weeks 12 to 28
- Progression of CKD: rate of change in eGFR over time adjusted by baseline eGFR, censored at dialysis or kidney transplant
- Time to (and proportion of subjects who received) blood/RBC transfusion in the first 52 weeks of treatment
- Mean CFB in the SF-36 PF subscore averaged over Weeks 12 to 28
- Blood pressure effect
 - a. Mean CFB in mean arterial pressure (MAP) averaged over Weeks 20 to 28, measured as the mean of the triplicate measurements 5 minutes apart
 - b. Time to (and proportion of subjects with) worsened hypertension (defined as systolic BP ≥ 170 mmHg and an increase from baseline of ≥ 20 mmHg, OR diastolic BP ≥ 110 mmHg and an increase from baseline of ≥ 15 mmHg, confirmed by the mean of triplicate measurements 5 minutes apart)

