5.2.3 Full Analysis Set (FAS)

The FAS consists of all randomized/enrolled subjects who received at least one dose of study drug and have baseline and at least one post-dose Hb assessment. If actual treatment received differs from the randomized treatment arm, the randomized treatment arm will be used for analysis for the FAS except for analyses by maintenance dosing frequency which will be presented as-treated. This analysis set is primarily used for EX-US submissions.

FAS1 is a subset of FAS subjects who are randomized/enrolled prior to Amendment 2. FAS2 is a subset of FAS subjects who are randomized/enrolled under Amendment 2 or later.

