5.3 METHODOLOGY AND CONVENTIONS

Continuous variables will be presented by descriptive statistics: n, mean, standard deviation, median, minimum, and maximum. Categorical variables will be presented by frequency count and percentage.

Lab results obtained from the central laboratory, rather than local laboratories, will be used for all efficacy and safety analyses. Local laboratory values, if collected in the CRF's, will be listed.

The treatment groups will be presented as follows:

Roxadustat QW(1A), Roxadustat BIW(2A), Roxadustat TIW(3A), Pooled Roxadustat (1A+2A+3A), Pooled Placebo (1P+2P+3P). Most safety and efficacy tables will be presented by Pooled Roxadustat vs. Pooled Placebo. Selected safety and efficacy tables will present randomized treatment arms of QW, BIW and TIW if the patient received the actual maintenance dosing frequency for QW, BIW and TIW. In these tables, Roxadustat subjects who were randomized to BIW or QW under Amendment 1 but never switched (e.g., due to Amendment 2) to that maintenance frequency will not be presented in BIW or QW group, but in the TIW and pooled Roxadustat groups.

The statistical comparisons will be done between roxadustat against Placebo as deemed appropriate, where the groups before amendment 2 are pooled

Unless otherwise stated, all statistical tests will be two-sided hypothesis tests performed at the 5% level of significance for main effects and all confidence intervals will be two-sided 95% confidence intervals.

The primary and secondary endpoints will be tested sequentially using the fixed sequence approach for multiplicity adjustments at an alpha level of 0.05. There will be no adjustments for multiple comparisons for other tests.

All analyses will be performed using SAS[®] Version 9.1.3 or higher.

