12.3 ANALYSES OF SECONDARY EFFICACY ENDPOINTS

The secondary efficacy endpoints will be analyzed using the FAS population as the primary analysis population for superiority, and PPS the primary analysis set for non-inferiority.

Secondary endpoints will be tested using a fixed sequence approach to adjust for multiple endpoints comparing between pooled roxadustat vs. pooled placebo, unless otherwise specified. If a null hypothesis is rejected, the claim of roxadustat over placebo will be declared successful and the test will progress to the next comparison in sequence.

1. Ex-US submission only: Mean CFB in Hb averaged over 8 weeks of treatment at Weeks 28 to 36, without rescue therapy within 6 weeks prior to and during this 8-week evaluation period for the two treatment groups will be compared using an MMRM model with baseline Hb and eGFR as covariates and treatment group, visit, treatment*visit, and the other

- randomization stratification factors as fixed effects. The same strategy as that used in MMRM for primary endpoint will be used to choose variance covariance structure. Data up to visit of Week 52 will be included in the model. The estimates for difference of Hb CFB averaged over Weeks 28 to 36 between the two treatment groups will be generated from an estimate statement for Weeks 28 to 36. Superiority will be declared if the lower bound of the 2-sided 95% confidence interval of the difference between roxadustat and placebo exceeds 0. Missing values will be handled by the MMRM model.
2. Mean CFB in Hb averaged over Weeks 28 to 52 in a subgroup of subjects with baseline CRP>ULN for the two treatment groups will be compared using MI ANCOVA model with baseline Hb as a covariate and treatment group, visit, treatment*visit, and the above-mentioned stratification factors as fixed effects. Data up to visit of Week 52 will be included in the model. The estimates for difference of Hb averaged over Weeks 28 to 52 between the two treatment groups will be generated from an estimate statement from Visit Week 28 to 52. Superiority will be declared if the lower bound of the 2-sided 95% confidence interval of the difference between roxadustat and placebo exceeds 0.
 3. Proportion of subjects with Hb (averaged Weeks 28 to 36) ≥ 10 g/dL, without use of rescue therapy within 6 weeks prior to and during this 8-week evaluation period, will be compared using Cochran-Mantel-Haenszel (CMH) adjusting for the randomization stratification factors.

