 4. To assess the effect of maintenance dosing frequencies, pairwise comparisons of roxadustat TIW (3A), BIW and QW (2A and 1A from the original and amendment 1 versions of the protocol) vs. pooled placebo (1P+2P+3P) will be performed in subjects treated with roxadustat who have achieved Hb response (achieved Hb ≥ 11 g/dL and Hb ≥ 1 g/dL at two consecutive visits) within the first 24 weeks of treatment, and were treated in the maintenance phase at dose frequencies of TIW, BIW, or QW after Hb response. The Hb levels of these patients will be analyzed by dose frequency during Hb maintenance phase vs pooled placebo for the following two endpoints in a fixed sequence:
 - Average Hb level over Weeks 28 to 36 in the roxadustat Hb maintenance dose frequency subgroup (e.g., TIW) vs pooled placebo using the same method for the US primary endpoint.
 - Proportion of subjects with Hb (averaged over Weeks 28 to 36) ≥ 10 g/dL in the roxadustat Hb maintenance dose frequency subgroup (e.g., TIW) vs. pooled placebo using the same method for the ex-US primary endpoint.
 - 1) Roxadustat TIW vs. pooled placebo,
 - 2) Roxadustat BIW vs. pooled placebo,
 - 3) Roxadustat QW vs. pooled placebo.
 5. Mean CFB in LDL cholesterol averaged over Weeks 12 to 28 for the two treatment groups will be compared using MMRM models with baseline LDL cholesterol as a covariate and treatment group, visit, treatment*visit, and the above-mentioned stratification factors as fixed

effects. The same strategy as that used in MMRM for Hb will be used to choose variance covariance structure. Data up to visit of Week 52 will be included in the model. The estimates for difference of LDL Cholesterol averaged over Weeks 12 to 28 between the two treatment groups will be generated from an estimate statement from Visit Week 12 to 28. Superiority will be declared if the lower bound of the 2-sided 95% confidence interval of the difference between roxadustat and placebo exceeds 0.

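### SAP secondary item 4 compares roxadustat responders with all placebo inside the alpha-controlled sequence, so a BIW or QW maintenance claim would partly reflect selection on earlier Hb

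*SAP*

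**What the plan says.** SAP 12.3, item 4, sets out to assess the maintenance dosing frequencies. Its comparisons "vs. pooled placebo (1P+2P+3P) will be performed in subjects treated with roxadustat who have achieved Hb response" in the first 24 weeks and were then treated at TIW, BIW or QW. Each group is set against the whole pooled placebo group on mean Hb, and on the proportion with Hb of at least 10 g/dL, both over Weeks 28 to 36.

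Under the original protocol and Amendment 1, response comes before conversion (SAP 3.1): "Once these criteria are met, a dose frequency conversion to QW or BIW or a continuation of TIW will occur". Frequency groups follow treatment received: SAP 5.2.3 uses randomised arms "except for analyses by maintenance dosing frequency which will be presented as-treated". Under SAP 5.3, in selected tables, subjects assigned to BIW or QW who never switched "will not be presented in BIW or QW group, but in the TIW and pooled Roxadustat groups".

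The item is confirmatory. SAP 4.2 lists "Hb maintenance by dose frequency: TIW, BIW, QW" as a secondary endpoint. SAP 5.3 states: "The primary and secondary endpoints will be tested sequentially using the fixed sequence approach for multiplicity adjustments at an alpha level of 0.05". Item 4 itself tests each frequency "vs pooled placebo for the following two endpoints in a fixed sequence". On rejection, SAP 12.3 says "the claim of roxadustat over placebo will be declared successful and the test will progress to the next comparison in sequence".

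The protocol differs. For secondary endpoints (9.4.3.2) it keeps BIW and QW comparisons exploratory or descriptive. In the FDA primary analysis (9.4.3.1) it plans a fixed sequence through TIW, BIW and QW against pooled placebo, with no response filter. SAP 12.1 tests only the pooled contrast for that endpoint and evaluates frequency alongside it in the FAS.

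**The concern.** Only the roxadustat side is filtered on a post-randomisation event, and that event is defined by Hb itself. A subject assigned to BIW or QW who does not respond is never in those groups, while the comparable placebo subject stays in. Rejection would show that roxadustat responders later have higher Hb than unselected placebo. It would not isolate what assignment to that frequency achieves.

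The exposure is mainly BIW and QW. Item 4 is reached only after pooled roxadustat has succeeded in earlier steps, including item 3 (and item 1 for the ex-US submission) at Weeks 28 to 36, so a null TIW result is remote. The case that matters is a drug that works overall while BIW or QW maintenance does not, which is what item 4 is meant to examine. Even if every frequency works, the estimate includes the selection component.

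**Working it through.** **Inputs from the documents.** SD 1.2 g/dL, 35 roxadustat vs 150 placebo, planning difference 0.75 g/dL, roxadustat response of at least 65% (SAP 5.1); a 91% response rate in one Phase 2 cohort (Protocol 2.5.2).

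**Assumptions, not in the documents.** r, the correlation between the early Hb that determines response and Hb at Weeks 28 to 36: 0.3, 0.5, 0.7. b, the correlation of baseline Hb with both early and late Hb: 0.3 or 0.5. An 80% response rate as an intermediate case.

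**Plan's own figure.** Standard error = 1.2 × √(1/35 + 1/150) = 0.225. 0.75 / 0.225 = 3.33. Power ≈ Φ(3.33 − 1.96) = 91.5% (91.2% with the t distribution), which agrees with the stated 90%.

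**Null.** All subjects assigned to the frequency, including non-responders who never convert, have the same Weeks 28 to 36 Hb distribution as placebo. The analysed group is the top fraction p on early Hb.

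**Selection shift, unadjusted.** Shift = 1.2 × r × k, where k = φ(z)/p and z = Φ⁻¹(1 − p).
- p = 0.65: z = −0.385, φ(z) = 0.370, k = 0.570. Shift 0.21, 0.34, 0.48 g/dL at r = 0.3, 0.5, 0.7.
- p = 0.80: k = 0.350. Shift 0.13, 0.21, 0.29 g/dL.
- p = 0.91: k = 0.178. Shift 0.06, 0.11, 0.15 g/dL.

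**Selection shift, baseline-adjusted.** For mean Hb, item 4 borrows the US primary method, which has baseline Hb and eGFR as covariates (SAP 12.1). The selected group's baseline mean is raised by b × k standard deviations, and the model removes about b times that. So adjusted shift ≈ 1.2 × k × (r − b²). At p = 0.65, 1.2 × k = 0.684:
- r = 0.3: 0.684 × 0.21 = 0.14 (b = 0.3); 0.684 × 0.05 = 0.03 (b = 0.5).
- r = 0.5: 0.684 × 0.41 = 0.28; 0.684 × 0.25 = 0.17.
- r = 0.7: 0.684 × 0.61 = 0.42; 0.684 × 0.45 = 0.31.
- r = 0.2, b = 0.5: 0.684 × (0.20 − 0.25) = −0.03, against roxadustat.

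**Two-sided rejection at 5%, by simulation, 35 vs 150.**

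| Responders | r | Unadjusted | Adjusted, b = 0.3 | Adjusted, b = 0.5 |
|---|---|---|---|---|
| 65% | 0.3 | 14% | 10% | 6% |
| 65% | 0.5 | 32% | 27% | 14% |
| 65% | 0.7 | 59% | 51% | 38% |
| 80% | 0.3 | 9% | 7% | 5% |
| 80% | 0.5 | 14% | 13% | 8% |
| 80% | 0.7 | 25% | 21% | 16% |

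Repeat runs with other seeds moved these rates by up to about two percentage points. With r = 0 the unadjusted test rejects 4.8%. At 91% responders the unadjusted rates are about 6% to 9% for r from 0.3 to 0.7.

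**Limits.** These are single-test rates for mean Hb, given that the test is reached. Baseline eGFR and the multiple imputation are not modelled. The Hb ≥ 10 g/dL endpoint borrows the CMH test, where screening Hb enters only as ≤ 8 vs > 8 g/dL, so baseline adjustment there is coarser. The SAP does not say how two endpoints and three frequencies are ordered within the step, so no joint rate is given.

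**The case against.** The strongest reply is that maintenance exists only after response, so conditioning on response is natural. That justifies a descriptive account of responders; it does not justify a superiority claim against a placebo group that keeps its non-responders.

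The objections to size carry more weight. The mean-Hb test is a baseline-adjusted ANCOVA, so the unadjusted rates overstate the problem whenever baseline predicts both early and late Hb. This stands, and the adjusted columns are the ones to use. The null is also demanding: at least 65% of an arm responds on active drug, yet the whole arm matches placebo a few weeks later. Early response may partly reflect drug sensitivity, which need not predict later Hb once the drug effect is assumed absent. Values of r of 0.5 to 0.7 are therefore only weakly supported.

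Two stronger readings are tempting. A reader might put the 25% placebo response rate of SAP 5.1 into the same formula and infer false-positive rates of 53% or more from r = 0.3 upward. The documents do not support this: item 4 filters roxadustat subjects, planned at 65% or more, and is reached only after pooled roxadustat has succeeded. A reader might also infer that the bias favours roxadustat at any positive r. Under the planned model it does so only when early and late Hb are positively correlated given baseline, in this set-up r > b².

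**Conclusion.** The concern holds as a flaw in a stated rule. Item 4 is a non-randomised contrast placed where rejection becomes a declared claim, and nothing elsewhere in the SAP removes the asymmetry; repeating the analysis in the ITT set (SAP 5.2.4) leaves the response filter in place.

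Confidence is high on the design and low on the size. At 65% responders, with baseline adjustment, selection alone is worth about 0.03 to 0.42 g/dL over r of 0.3 to 0.7 and b of 0.3 to 0.5, that is 5% to 56% of the 0.75 g/dL planning difference. Rejection runs from near nominal (6%) to 51%. It is close to nominal when the correlation given baseline is low, and smaller throughout when response rates are higher.

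Both primary endpoints, items 1 to 3 and the pooled comparisons in items 5 to 12 are not biased by this, although whether items 5 onward are reached depends on item 4. The documents do not support reading this as a threat to the overall efficacy conclusion. It should be fixed before unblinding.

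**What to change.** Either change removes the problem, and both need SAP wording only.

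**(a) Take item 4 out of the fixed sequence.** Item 3 then leads to item 5. State in 12.3 that the responder-only, as-treated results by frequency are summarised descriptively, with no superiority claim against unselected placebo. Move the endpoint on Hb maintenance by dose frequency from SAP 4.2 to 4.3, because SAP 5.3 puts every secondary endpoint in the sequence. Cost: no alpha-controlled claim by frequency remains, since SAP 12.1 has already dropped those steps from the FDA primary test.

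**(b) Keep a controlled step without the response filter.** Compare the as-randomised pre-Amendment 2 arms (1A, 2A, 3A, within ITT1 or FAS1) with concurrently randomised placebo, and state the order of endpoints and frequencies. This is closer to the protocol's unfiltered FDA sequence. In simulations with no drug effect, comparing all randomised subjects gave type I error of 5.0% to 5.7%. With 100 vs 150 (SAP Table 1) and only the 65% who respond gaining 0.75 g/dL, the difference is 0.65 × 0.75 = 0.49 g/dL and power is about 88%; the numbers actually enrolled before Amendment 2 are not in the documents. Cost: some power, and the test concerns assignment to a frequency rather than frequency received. The SAP should say that subjects kept on TIW by Amendment 2 (SAP 3.2) dilute the contrast, and report how many there were.

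Under either option, correct the pointer in item 12 to the approach in item 4, which contains no hazard model.

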 - Number of ESA-week dose per PEY: 1-3 doses of epoetin alfa or beta or biosimilar thereof (in Europe) administered within 1 week = 1 ESA-week; 1 darbepoetin subcutaneous (SQ) or IV dose = 2 ESA-week; 1 Mircera IV or SQ dose = 4 ESA-week
 - Time to (and proportion of subjects who receive) IV iron therapy in the first 24 weeks of treatment, and in treatment period
 - IV iron(mg) per patient-month (4 weeks) exposure to study medication
 - Exposure adjusted incidence rate of rescue therapy (composite, and individual component) per PEY, overall and sub-grouped by baseline Hb (≤ 8 g/dL, >8 g/dL)

Changes in cholesterol levels

- Change from baseline at each of the selected treatment time points (averaged over Weeks 12-28, and Week 36, 44 and 52) in:
 - Total cholesterol
 - Low-density lipoprotein/high-density lipoprotein ratio
 - Non-HDL cholesterol
- Proportion of subjects achieving LDL target of < 100 mg/dL for average LDL over Weeks 12 to 28

Blood pressure effect

- Proportion of subjects achieving blood pressure treatment goal in CKD subjects (systolic BP < 130 mmHg systolic and diastolic BP < 80 mmHg) based upon the average blood pressures over Weeks 12 to 28 of treatment

Health-Related Quality of Life (HRQoL) and European Quality of Life in Five Dimensions, Five Levels (EQ-5D-5L) benefits of anemia therapy in subjects with CKD anemia

- Mean CFB averaged over Weeks 12 to 28 of treatment in:
 - Vitality Subscale of SF-36
 - In subjects with baseline VT subscore below 50
 - Physical Functioning (PF) Subscale of SF-36
 - In subjects with baseline PF subscore below 50
 - Physical Component Scores of SF-36
 - In subjects with baseline physical component scores below 40
 - In all subjects

- Other component scores of SF-36
 - In all subjects
- Anemia Subscale (“Additional Concerns”) of Functional Assessment of Cancer Therapy-Anemia (FACT-An) Scores
 - In subjects with baseline subscale scores below 55 (generally associated with fatigue.)
 - In all subjects
- Total FACT-An Scores
 - In subjects with baseline FACT-An scores below 135
 - In all subjects
- EQ-5D-5L Scores
 - In all subjects

Hepcidin, CHr, Iron Parameters, HbA1c, and CKD Progression

- Change from baseline in serum hepcidin at each scheduled time point up to Week 52
- Change from baseline in CHr at each scheduled time point up to Week 52

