hemoglobin for the treatment group minus the least-squares mean CFB in hemoglobin for the placebo group) and the corresponding p-values and 95% CIs during the evaluation period.

For Ex-US Submission

The primary EX-US efficacy endpoint will be analyzed using the FAS population as the primary analysis population.

The primary efficacy endpoint for the Ex-US submission of proportion of responders will be compared using Cochran-Mantel-Haenszel (CMH) adjusting for the randomization stratification factors comparing the pooled roxadustat (TIW+BIW+QW) to pooled placebo (TIW+BIW+QW). The hypothesis to be tested for the primary efficacy analysis is:

H₀: Hb responder rate in the roxadustat group = Hb responder rate in Placebo group

Versus:

H₁: Hb responder rate in the roxadustat group ≠ Hb responder rate in Placebo.

H₀ will be tested at the two-sided alpha = 0.05 level of significance and will be rejected if the p < 0.05 from the test.

The SAS procedure will be similar to the following:

```
proc freq;
  tables covariates*Treatment*Response / cmh;
run;
```

The 95% CIs based on CMH adjusted odds ratio will be reported. In addition, the 95% CIs of the responder rate and rate difference between treatment groups based on the exact method of Clopper-Pearson will be calculated and presented.

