6. Time to rescue therapy (composite of blood/RBC transfusion, ESA use, and IV iron) in the first 52 weeks of treatment will be compared using Inverse Probability of Censoring Weighted (IPCW) model detailed in Appendix A or Cox Proportional Hazards model as deemed appropriate. The Cox regression model will adjust for baseline Hb, baseline eGFR and other randomization stratification factors. Hazard ratio and its associated 95% CI will be computed between the roxadustat group versus pooled placebo. Superiority will be declared if the upper bound of the 2-sided 95% CI of the hazard ratio does not exceed one. Proportion of subjects who received rescue therapy over the treatment period will be derived using Kaplan-Meier approach.
7. Mean CFB in the SF-36 Vitality subscore averaged over Weeks 12 to 28 for the two treatment groups will be compared using an MMRM model as outlined above. A subgroup of subjects with baseline vitality subscore below 50 will be analyzed as a sensitivity analysis.
8. Progression of CKD measured by rate of change in eGFR over time adjusted by baseline eGFR, censored at chronic dialysis or kidney transplant will be analyzed using random slope and intercept model. Annualized eGFR slope over time is estimated by a random slope and intercept model using all available eGFR values (one baseline and all post-treatment values up to End of Treatment Period or start of chronic dialysis or kidney transplant) adjusted by Baseline Hb, Region, CV history at Baseline and the interaction terms Baseline eGFR by time point and Baseline Hb by time point). All assessments collected after initiation of chronic dialysis or kidney transplant will be excluded from the analysis.
9. Time to blood/RBC transfusion in the first 52 weeks of treatment will be compared using Inverse Probability of Censoring Weighted (IPCW) model detailed in Appendix A or Cox Proportional Hazards model as deemed appropriate. The Cox regression model will adjust for baseline Hb, baseline eGFR and other randomization stratification factors. Hazard ratio and its associated 95% CI will be computed between the roxadustat group versus pooled placebo. Superiority will be declared if the upper bound of the 2-sided 95% CI of the hazard ratio does not exceed one. Proportion of subjects who received blood/RBC transfusion over the treatment period will be derived using Kaplan-Meier approach.

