10. Mean CFB in the SF-36 PF subscore averaged over Weeks 12 to 28 for the two treatment groups will be compared using an MMRM model as outlined above. A subgroup of subjects with baseline PF subscore below 50 will be analyzed as a sensitivity analysis.
11. Mean CFB in MAP averaged over Weeks 20 to 28 for the two treatment groups will be compared using an MMRM model as outlined above with a non-inferiority margin of 5.

12. Time to (and proportion of subjects with) protocol defined worsened hypertension for the pooled roxadustat vs pooled placebo will be compared using the approach in #4 above. Hazard ratio and its associated 95% CI will be computed between the roxadustat group versus pooled placebo. Non-inferiority will be declared if the upper bound of the 2-sided 95% CIs of the odds ratio does not exceed 1.3. Superiority will be declared if the upper bound of the 2-sided 95% CI of the hazard ratio does not exceed one. The incidence rate per PEY by treatment group will also be reported.

In MMRM above, due to large amount of visits to include in the model, the unstructured covariance pattern model will be applied first. If the algorithm for unstructured covariance pattern does not converge, then the heterogeneous Toeplitz structure will be used instead. If this second model also does not converge, then the (homogeneous) Toeplitz structure will be tried, and finally compound symmetry as a covariance structure to achieve convergence. If none of them converge, first order autoregressive (AR (1)) as a covariance structure will be used to achieve convergence.

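### SAP 12.3 item 5 tests LDL superiority in the wrong direction: read as roxadustat minus placebo, an LDL reduction cannot be declared superior and an increase can

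*SAP*

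**What the plan says.** SAP 12.3 lists twelve secondary items to be tested in a fixed sequence. Item 5 compares mean change from baseline in LDL, averaged over Weeks 12 to 28, by MMRM. It ends: "Superiority will be declared if the lower bound of the 2-sided 95% confidence interval of the difference between roxadustat and placebo exceeds 0". Items 1 and 2, both on haemoglobin change, carry the same sentence.

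Other places that bear on it:

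- **Order of subtraction.** SAP 12.1 describes the treatment effect, as an example for the haemoglobin primary analysis, as the least-squares mean change in "hemoglobin for the treatment group minus the least-squares mean CFB in hemoglobin for the placebo group". No other order is given anywhere, and none is given for LDL.
- **Direction of benefit.** SAP 4.3 lists "Proportion of subjects achieving LDL target of < 100 mg/dL for average LDL over Weeks 12 to 28" among the additional efficacy evaluations. Protocol 8.3 has the same target, and protocol 2.4 names a better lipid profile as a potential advantage of the drug.
- **Progression rule.** The introduction to SAP 12.3 says: "If a null hypothesis is rejected, the claim of roxadustat over placebo will be declared successful and the test will progress to the next" comparison. SAP 5.3 adds that, unless otherwise stated, "all statistical tests will be two-sided hypothesis tests performed at the 5% level of significance".
- **Endpoints where fewer events are better.** Item 6 (rescue therapy) reads: "Superiority will be declared if the upper bound of the 2-sided 95% CI of the hazard ratio does not exceed one". Items 9 and 12 also use the upper bound.
- **Protocol.** Section 9.4.3.2 item 2 specifies an MMRM for LDL and gives no confidence-bound criterion.

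**The concern.** A lower bound above 0 is the right test when a positive difference is the benefit, as for haemoglobin. Applied to LDL with the same order of subtraction, it rewards an increase. The likely cause is haemoglobin text carried into item 5.

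Two things are at stake. First, the LDL claim itself: as written, item 5 denies superiority after a reduction and grants it after an increase. Second, the sequence: the SAP does not say whether item 5's bound or a two-sided p-value decides progression to item 6. If the bound decides, an LDL reduction ends formal testing of rescue therapy, SF-36 Vitality, eGFR slope, transfusion, SF-36 PF, MAP and worsened hypertension. If the p-value decides, those tests proceed, but the general rule calls the LDL claim successful while item 5 denies it. Choosing between the two after unblinding would be a data-dependent decision.

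**Working it through.** **Step 1. Does the text force the direction?** Items 1, 2 and 5 use identical words for the difference. In items 1 and 2 the sentence makes sense only as roxadustat minus placebo, which matches the one order SAP 12.1 spells out. Item 5 would be right only if the same words, in the same list, meant placebo minus roxadustat. Nothing says so. Items 6, 9 and 12 show that the SAP does set the bound by endpoint.

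**Step 2. What the rule does, with no assumed values.** Let d be the true difference (roxadustat minus placebo) and SE its standard error. By normal approximation:

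- Rule as written: P(lower bound > 0) = 1 − Φ(1.96 − d/SE)
- Reversed rule: P(upper bound < 0) = Φ(−1.96 − d/SE)

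At d = 0 both equal 0.025. The first falls as d becomes more negative, so for any true reduction it is at most 2.5%. An interval wholly below 0 fails the written rule by definition. Reversing the bound leaves the error rate under no effect at 2.5% in the tested direction.

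**Step 3. Illustration.** The documents give no LDL effect, SD or power, so there is no plan figure to reproduce. Assumed: SD 30 or 40 mg/dL and the values of d below. From SAP 5.1: 300 vs 150 (minimum) and 800 vs 400 (maximum). SE = SD × √(1/n₁ + 1/n₂):

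- 300 vs 150: 30 × √(1/300 + 1/150) = 3.00; with SD 40, 4.00
- 800 vs 400: 1.84 and 2.45
- 210 vs 105 (30% of subjects removed, an assumption): 3.59 and 4.78

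| n | True d (mg/dL) | Written rule, SD 30 / 40 | Upper bound < 0, SD 30 / 40 |
|---|---|---|---|
| 300 vs 150 | −5 | 0.014% / 0.066% | 38.5% / 23.9% |
| 300 vs 150 | −10 | 6.0e-8 / 4.1e-6 | 91.5% / 70.5% |
| 300 vs 150 | −15 | 1.7e-12 / 5.7e-9 | 99.9% / 96.3% |
| 800 vs 400 | −5 | 1.4e-6 / 3.2e-5 | 77.7% / 53.2% |
| 800 vs 400 | −10 | 6.6e-14 / 7.6e-10 | 99.98% / 98.3% |
| 210 vs 105 | −10 | 1.0e-6 / 2.5e-5 | 79.6% / 55.2% |

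Entries without a percent sign are probabilities. Worked example at 300 vs 150, SD 30, d = −10: d/SE = −3.33; written rule 1 − Φ(5.29) = 6.0e-8; reversed rule Φ(1.37) = 0.915. By symmetry, a true increase of 10 mg/dL at 300 vs 150 would be declared superior with probability 91.5% (SD 30) or 70.5% (SD 40).

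**Step 4. Effect on the sequence after an LDL reduction.** Seven items follow LDL (6 to 12). If item 5's bound is the gate, all seven are lost to formal testing. If the gate is a two-sided p-value, a significant reduction loses none.

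**The case against.** The best reply is that progression is less open than it looks. The SAP 12.3 introduction moves on when a null hypothesis is rejected, SAP 5.3 makes tests two-sided by default, and items 3, 4 and 8 have no confidence-bound criterion at all, so rejection of the null is the only gate that works across the whole list. On that reading a significant LDL reduction opens item 6, and the damage is one contradictory sentence about one secondary claim. The intended direction is plain from the LDL target, and the order of subtraction is an inference from an example given for haemoglobin.

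Much of this stands. The p-value reading of the gate is the more natural one, and the order is inferred. It is also fair that every probability apart from the 2.5% ceiling rests on assumed values and treats an MMRM average over several visits as a single comparison of means.

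It does not remove the error. SAP 5.3 yields where something else is stated, and item 5 states something else, so the bound remains a possible gate. On the p-value reading, the SAP still both grants and denies the LDL claim after a reduction, and a two-sided rejection caused by an increase would satisfy both sentences. That readers can guess the intent is a reason to correct the text while the data are still blinded.

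**Conclusion.** The concern holds. Read as roxadustat minus placebo, item 5 cannot be met by a demonstrated LDL reduction and can be met by an increase. For any true reduction the chance of meeting it is at most 2.5%, with no effect or SD assumed; the mg/dL figures are illustrations only. The one textual assumption is the order of subtraction, which rests on SAP 12.1 and on items 1 and 2, with nothing in either document pointing the other way.

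Loss of items 6 to 12 depends on the bound being the gate, which the SAP leaves unsettled; under a two-sided p-value no later step is lost after a significant reduction. Both primary endpoints are untouched. It must be fixed because it is a written decision rule in the alpha-controlled sequence that gives the wrong answer if followed.

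**What to change.** Replace the last sentence of item 5 with: superiority is declared if the upper bound of the two-sided 95% CI of the difference (roxadustat minus placebo) in LDL change from baseline averaged over Weeks 12 to 28 is below 0, and this criterion is the gate for item 6.

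At the same time, state the direction for the two SF-36 items. Item 7 says "SF-36 Vitality subscore averaged over Weeks 12 to 28 for the two treatment groups will be compared using an MMRM model as outlined above", and item 10 says "SF-36 PF subscore averaged over Weeks 12 to 28 for the two treatment groups will be compared using an MMRM model as outlined above". Higher SF-36 scores are better (protocol 7.7.1), so for both the difference should be roxadustat minus placebo with the lower bound above 0. Correcting item 5 alone would risk carrying the LDL direction into them. Item 11 (MAP) uses the same cross-reference with a margin of 5 and no stated direction, so its order of subtraction and bound are worth stating too.

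The cost is a few sentences in the SAP before database lock. No new data or analyses are needed, and alpha and sample size do not change.
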